#### Change from baseline to Week 24 in reported Visual analogue scale (VAS) for rhinosinusitis

The VAS for rhinosinusitis is used to evaluate the total severity (4) based on the distance (cm) from 0 to a subject's response to the following question:

“How troublesome are your symptoms of your rhinosinusitis?”

The response can be categorized as MILD, MODERATE, and SEVERE based on total severity VAS score [0 (Not troublesome) to 10 cm (Worst thinkable troublesome)]:

- MILD = VAS 0 to 3 cm
- MODERATE = VAS  $>3$  to 7 cm
- SEVERE = VAS  $>7$  to 10 cm

#### **4.4.2.2 Main analytic approach**

The supportive secondary efficacy endpoints (TSS, Loss of smell severity, VAS) will be analyzed using similar methodology as the key secondary endpoints using the PP population. Additionally, the number and percent of participants with VAS scores  $\leq 7$  cm will be presented using similar methodology for intercurrent events as the primary endpoint (Estimand 1).

### **4.5 TERTIARY/EXPLORATORY ENDPOINTS ANALYSIS**

#### **4.5.1 Tertiary/Exploratory Endpoints**

- Proportion of participants with NPS improvement from baseline  $\geq 1$  at Week 52
- Change from baseline to Week 52 in bilateral NPS
- Change from baseline to Week 52 in NC symptom severity score using the CRSwNP nasal symptom diary
- Change from baseline to Week 52 in opacification of sinuses assessed by CT scan using the LMK score
- Change from baseline to Week 52 in TSS
- Same as primary and secondary endpoints

## **4.5.2 Main Analytical approach**

### **4.5.2.1 Proportion of participants with NPS improvement from baseline $\geq 1$ at Week 52**

The number of participants and percentage with the 95% continuity corrected Wilson confidence interval (CI) will be provided at Week 52 in the PPE analysis population, similar to the primary endpoint (Estimand 1).

Participants who are rescued (undergo surgery for NP or receive SCS for any reason) will be considered nonresponders for time points after rescue. Participants who have missing data at Week 52 will be considered nonresponders.

### **4.5.2.2 Change from baseline to Week 52**

Descriptive statistics for the exploratory efficacy endpoints (NPS, NC symptom severity score, LMK score, and TSS at Week 52) will be presented by dose regimen group and overall using the PPE analysis population.

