9.1 SAMPLE SIZE DETERMINATION

In EFC14280, the proportion of responders (NPS improvement from baseline ≥ 1) at Week 24 was 62.0% in the dupilumab group. Based on this result, the proportion of responders (NPS improvement from baseline ≥ 1) at Week 24 in this postmarketing study will be at least 50.0% to justify the similar effect size between EFC14280 and this study.

It is necessary for 20 participants to achieve this similar responder rate (at least 50%) with a 90% probability of success. The sample size was adjusted up to 25 to account for a 20% drop-out rate.

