Key secondary endpoints	Change from baseline to Week 24: 
 
• Bilateral NPS
 
• NC symptom severity score
 
• LMK score
 
	PP	The intercurrent events will be handled as follows: 
 
• Taking rescue medications or undergo surgery prior to Week 24: data will be set to missing after the medication usage, and the participant's worst postbaseline value on or before the time of the medication usage or surgery will be used to impute the missing Week 24 value (for participants whose postbaseline values are all missing, the baseline will be used to impute) (hypothetical strategy)
 
• Discontinuing the treatment prematurely (Participants who did not take rescue medications or undergo surgery): all data collected after treatment discontinuation will be used in the analysis (treatment policy strategy).
 
	All imputed, complete data will be analyzed by descriptive statistics and 95% CI. The summarized mean changes obtained from each imputed dataset will be combined using Rubin's rule for a single estimate.

Estimands				
Endpoint Category	Endpoint	Population	Intercurrent event(s) handling strategy (The missing data handling)	Population-level summary (Analysis method)
Other secondary efficacy endpoints	
 
• Change from baseline to Week 24:
 
• Total symptom score
 
• Loss of smell symptom severity score
 
 Visual analogue scale for rhinosinusitis		In addition, the missing data imputation rules are as follows: 
 
• After treatment discontinuation due to lack of efficacy prior to Week 24: WOCF approach will be used to impute the missing Week 24 value if needed
 
• After treatment discontinuation due to reasons other than lack of efficacy prior to Week 24: multiple imputation approach assuming missing at random will be used to impute the missing Week 24 value, and this multiple imputation will use all participants, excluding participants who have taken rescue medications or undergone surgery on or before Week 24 and excluding participants who discontinue due to lack of efficacy on or before Week 24.
 
	

Estimands				
Endpoint Category	Endpoint	Population	Intercurrent event(s) handling strategy (The missing data handling)	Population-level summary (Analysis method)

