	Proportion of participants with NPS improvement from baseline $\geq 1$ at Week 52	PPE	
The intercurrent events will be handled as follows:
 
 
Undergoing surgery for NP or receiving SCS for any reason will be considered nonresponders for time points after undergoing surgery or receiving SCS. (composite strategy)
 
 
In addition, the missing data imputation rules are as follows: Patients having missing data at Week 52 will be considered nonresponders..
	Descriptive statistics
	
Change from baseline to Week 52 in:
 
 
Bilateral NPS
 
NC symptom severity score
 
LMK score
 
TSS score
 
		
The intercurrent events will be handled as follows:
 
 
Taking rescue medications or undergo surgery for NP prior to Week 52: data will be set to missing after the medication usage, and the participant's worst postbaseline value on or before the time of the medication usage or surgery will be used to impute the missing Week 52 value (for participants whose postbaseline values are all missing, the baseline will be used to impute) (hypothetical strategy)
 
Discontinuing the treatment (Participants who did not take rescue medications or undergo surgery): all data collected after treatment discontinuation will be used in the analysis (treatment policy strategy).
 
	Descriptive statistics

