## 2 SAMPLE SIZE DETERMINATION

The EFC14280 study, which was conducted as a pivotal study for Nasal Polyposis, the proportion of responders (NPS improvement from baseline  $\geq 1$ ) at Week 24 was 62.0% in the dupilumab group. Based on this result, the target proportion of responders (NPS improvement from baseline  $\geq 1$ ) at Week 24 in this postmarketing study is at least 50.0% to reflect the similar effect size between EFC14280 and this study.

It is necessary for 20 participants to achieve this response rate (at least 50%) with a 90% probability of success. The sample size was adjusted up to 25 to account for a 20% drop-out rate.

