## **4.6 MULTIPLICITY ISSUES**

No hypothesis testing will be performed within this study.

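### The exploratory Week 52 mean changes leave out a participant who stops for lack of efficacy, is not rescued and has no Week 52 value, although the Week 24 analysis would assign that person the worst value

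*SAP*

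**What the plan says.** SAP 4.5.2.2 covers the Week 52 mean changes in NPS, NC, LMK and TSS in one sentence: descriptive statistics "will be presented by dose regimen group and overall using the PPE analysis population". It does not mention missing values. Protocol 9.3.4 also asks for descriptive statistics and leaves the details to the SAP.

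The Week 52 mean-change row of SAP Table 3 adds two rules:
- After rescue medication or surgery, later data are dropped and the worst postbaseline value (baseline if there is none) "will be used to impute the missing Week 52 value".
- After a treatment stop without rescue, whatever is still collected is used.

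That row has no part on missing data. Neighbouring rows do. For the Week 24 mean changes: "After treatment discontinuation due to lack of efficacy prior to Week 24: WOCF approach will be used to impute the missing Week 24 value", with multiple imputation for stops for other reasons. For the Week 52 responder rate: "Patients having missing data at Week 52 will be considered nonresponders".

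SAP 4.5.2.3 then describes by-visit summaries of the primary and secondary endpoints up to Week 52 and rules out imputation for them.

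**The concern.** A participant who stops because the drug is not working, is not rescued and has no Week 52 value is a failure in the Week 52 responder rate but is absent from the Week 52 mean NPS change. The two results would then rest on different participants. The mean at Week 52 would also follow a more lenient rule than the mean at Week 24, so a comparison of the two could show a better maintained effect partly because failures had left the average.

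The four mean changes are four of the five efficacy endpoints listed for the 52-week objective, and they are shown by dose regimen. The q2w group includes everyone who did not reach stable disease at Week 24, so such stops may gather there, in a small denominator.

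**Working it through.** **The plan's own figure.** The only sizing figure concerns the Week 24 responder rate. Protocol 9.1 states that "the proportion of responders (NPS improvement from baseline ≥ 1) at Week 24 was 62.0% in the dupilumab group". SAP section 2 adds: "It is necessary for 20 participants to achieve this response rate (at least 50%) with a 90% probability of success"; and "The sample size was adjusted up to 25 to account for a 20% drop-out rate". For X binomial with n = 20 and p = 0.62, P(X >= 10) = 0.9077, and 20/(1 - 0.20) = 25. Both reproduce. Neither bears on the Week 52 means, for which the documents give no figure.

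**The rules side by side**, for a non-rescued stop for lack of efficacy with the value missing:

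| Analysis | Handling |
|---|---|
| Week 24 mean change (Table 3, SAP 4.4.1.2) | WOCF |
| Week 52 responder (Table 3, SAP 4.5.2.1) | nonresponder |
| Week 52 mean change (Table 3, SAP 4.5.2.2) | no rule, so left out |
| By-visit summaries to Week 52 (SAP 4.5.2.3) | no imputation, so left out |

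The imputation steps in SAP 4.4.1.2 run only through Week 24, so they cannot be read as covering Week 52.

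**Who can be missing.** PPE requires a dose after Week 24, so earlier stops do not matter here. Protocol 7.1.1 continues follow-up to the scheduled completion date, and Table 3 uses what is collected, so stopping alone removes nobody. A Week 52 value can still be absent:
- NPS: Protocol 7.1.1 asks for the end-of-treatment assessments as soon as possible after the stop. In SAP Table 10 the Week 52 endoscopy window opens at Day 322. An endoscopy on Days 225 to 321 counts as Week 40. Without a later visit, Week 52 is missing.
- LMK: the CT window opens at Day 266, but Protocol 7.1.1 excepts the CT scan after permanent discontinuation. LMK is therefore the most exposed endpoint.
- NC and TSS: SAP 4.4.2.1 needs diary entries on at least half of the days averaged before the visit.

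**Size, for illustration.** Let N be the number in PPE, k the number of such participants, m the mean change in the other N - k, and w the worst-value change. The documents give none of k, m or w, so all three are assumptions.

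Mean with WOCF = ((N - k)m + kw)/N. Shift = (k/N)(w - m).

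With N = 20, m = -2.0 and w = 0 (worst value equal to baseline):
- k = 1: (19 x -2.0 + 0)/20 = -1.90, a shift of 0.10
- k = 2: -1.80
- k = 3: -1.70
- k = 5: -1.50

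With w = +1 and k = 1: (19 x -2.0 + 1)/20 = -1.85, a shift of 0.15.

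Range over N = 20 to 25, k = 1 to 5, m = -1 to -3 and w = 0 to +1:
- smallest: (1/25)(0 + 1) = 0.04
- largest: (5/20)(1 + 3) = 1.0

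The shift is toward less improvement whenever w is worse than m.

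Within a regimen group the denominator is smaller. In an assumed q2w group of 8 with m = -1.5 and w = 0, one such participant shifts the mean by (1/8)(1.5) = 0.19 points and two by (2/8)(1.5) = 0.38.

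**The case against.** The strongest reply is that the SAP does take a position. Section 4.5.2.3 excludes imputation for the by-visit summaries to Week 52, and those cover the change endpoints as well as the responder rate. Observed-case means are a legitimate choice for exploratory endpoints in a single-arm study where "No hypothesis testing will be performed within this study". The failures also stay visible: SAP 4.2 tabulates non-completion, its main reasons and rescue separately for the two regimens, and the Week 52 responder rate counts every missing value as a failure.

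Much of this stands, and it sets the priority. It does not close the gap. The sentence in 4.5.2.3 belongs to the by-visit summaries. If it also governed 4.5.2.2, it would contradict the worst-value imputation after rescue that Table 3 prescribes for the same means. Either reading needs a correction.

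Two further objections also stand:
- WOCF is not the truth. It can carry a value from before response began, so the shift is a difference between two methods, not a proven bias.
- The Week 24 rule cannot be copied as it is. The narrative of SAP 4.4.1.2 uses data collected after a lack-of-efficacy stop, while its imputation steps set those data to missing.

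A reader might infer that the Week 52 means have no missing-data rule at all, or that everyone who stops treatment drops out of them. The documents do not support either: rescued participants have a rule, and a participant who stops but has a Week 52 value is included.

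**Conclusion.** The point holds in a narrow form. Table 3 and SAP 4.5.2.2 leave out of the Week 52 mean changes a PPE participant who stops for lack of efficacy after Week 24, is not rescued and has no Week 52 value. The same SAP gives that person WOCF at Week 24 and counts them as a Week 52 nonresponder.

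The omission favours the drug as long as the worst value is worse than the observed mean. Under the imputation steps of SAP 4.4.1.2, which let baseline count as the worst value, the assigned change cannot be an improvement. Under Table 3's postbaseline wording for rescue it could be, and the shift would be smaller.

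The size is unknown. About 0.10 NPS points per participant in 20 rests on an assumed observed mean of -2.0 and a worst value equal to baseline. A reader might infer a definite percentage overstatement of the 52-week effect, but the documents give neither the number of such stops nor the Week 52 means. The primary Week 24 result is not affected. This is a low-priority correction that the plan could make, because the endpoints are exploratory and descriptive.

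**What to change.** 1. In the Week 52 mean-change row of Table 3 and in SAP 4.5.2.2, assign WOCF to a missing Week 52 value after a non-rescued stop for lack of efficacy. Keep using any value actually collected after the stop.
2. Before re-using the steps in SAP 4.4.1.2, resolve their contradiction on data collected after such a stop, and say whether baseline can count as the worst value.
3. Show the observed-case mean beside the WOCF mean, with the number missing by reason and by regimen.
4. State that the no-imputation sentence in SAP 4.5.2.3 applies only to the by-visit summaries, so that it does not conflict with Table 3.

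Multiple imputation for other missing Week 52 values is optional. The cost is SAP wording and re-use of the Week 24 program, extended to Week 52. No new data are needed.

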6.5 DOSE MODIFICATION

For participants who have stable disease (NPS improvement from baseline to both Weeks 16 and 24 is ≥ 2 points), the dosing interval can be changed from q2w to q4w at the discretion of the Investigator at Week 24. Participants who proceed to the dosing interval from q2w to q4w will not be permitted to return to the q2w regimen during this study. The maximum dose will not exceed dupilumab 300 mg q2w.

However, any dose reduction is not allowed other than above.

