
 
To assess the efficacy of 52-week treatment with dupilumab under different dosing regimens to participants with CRSwNP who do not use concomitant INCS
 
To evaluate the safety of 52-week treatment with dupilumab in participants with CRSwNP
 
	
 
Proportion of participants with NPS improvement from baseline <math>\geq 1</math> at Week 52
 
Change from baseline to Week 52 in bilateral NPS
 
Change from baseline to Week 52 in NC symptom severity score using the CRSwNP nasal symptom diary
 
Change from baseline to Week 52 in opacification of sinuses assessed by CT scan using the LMK score
 
Change from baseline to Week 52 in TSS
 
Incidence of TEAEs, TESAEs, and TEAEs leading to treatment discontinuation
 

Abbreviations: CRSwNP: chronic rhinosinusitis with nasal polyposis; CT: computerized tomography; INCS: intranasal corticosteroid; LMK: Lund Mackay; NC: nasal congestion/obstruction; NPS: nasal polyp score; q2w: every 2 weeks; TEAE: treatment-emergent adverse event; TESAE: treatment-emergent serious adverse events, TSS: total symptom score

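### Week 52 results by regimen are all measured from the original baseline, while the q4w group is selected on NPS response at Weeks 16 and 24, so NPS favours q4w through selection and the course after the switch is not shown directly

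*SAP*

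**What the plan says.** The exploratory efficacy objective in SAP Table 2 is "To assess the efficacy of 52-week treatment with dupilumab under different dosing regimens" in participants not using INCS. Protocol 4.2.2 likewise announces Week 52 data for both regimens.

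Protocol 6.5 sets the gate to q4w. Stable disease means that NPS "improvement from baseline to both Weeks 16 and 24 is ≥ 2 points". For those participants "the dosing interval can be changed from q2w to q4w at the discretion of the Investigator at Week 24", and a return to q2w is not allowed. SAP 4.1 builds stable disease into the q4w group. Its q2w group is everyone dosed with q2w after Week 24 who never received q4w.

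The Week 52 outputs are:

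- **SAP 4.5.2.1:** the proportion improved by at least 1 point in the PPE population, with no regimen split named.
- **SAP 4.5.2.2:** change from baseline in NPS, NC, LMK and TSS, which "will be presented by dose regimen group and overall using the PPE analysis population".
- **SAP 4.5.2.3:** the primary and secondary endpoints at each visit, without imputation. The regimen split is stated for visits after Week 24 only.

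SAP 4.6 states: "No hypothesis testing will be performed within this study".

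**The concern.** The regimen groups are formed after treatment starts, using the same score that is later reported. People who had done well on NPS by Week 24 can enter q4w. People who had not done well stay on q2w. A Week 52 table that measures both groups from the original baseline carries that difference forward, whatever the longer interval does.

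The responder threshold adds to this. It is 1 point, below the 2-point entry rule, so a q4w participant can lose much of the benefit after the switch and still count as a responder.

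What is at stake is interpretation. A reader of the Week 52 table may conclude that q4w does as well as q2w, or better, when the table mainly reflects who was allowed to switch. Whether response is kept after the switch is the natural question about the extension, and no planned summary addresses it directly.

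**Working it through.** **1. The plan's own figure.** Protocol 9.1 reports that the EFC14280 responder rate "at Week 24 was 62.0% in the dupilumab group" and says: "It is necessary for 20 participants to achieve this similar responder rate (at least 50%) with a 90% probability of success". With X ~ Binomial(20, 0.62), P(X ≥ 10) = 0.908, which matches the stated 90%. For dropout, 20 / (1 − 0.20) = 25, which matches "The sample size was adjusted up to 25 to account for a 20% drop-out rate". These figures are not in dispute. The 62% anchors the illustration below.

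**2. Single-participant arithmetic.** Take an NPS improvement of 4 points at Week 24 and 1 point at Week 52. Change from baseline is −1 and the participant is a responder (1 ≥ 1). The loss since Week 24 is 4 − 1 = 3 points, and the participant no longer meets the entry rule (1 < 2).

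**3. Size of the selection effect with no regimen effect.**

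- *From the documents:* 62% responders, the 2-point gate at both visits, discretionary switching, 25 enrolled.
- *Assumed, because the documents do not give them:* SD of NPS improvement 1.5 to 2.0; between-visit correlation 0.5 to 0.9; all or half of stable participants switched.
- *Model:* improvement at Weeks 16, 24 and 52 = person effect + visit noise, normal, rounded to whole points, with the same mean at each visit. The mean is 0.5 + 0.3055 × SD, so that 62% improve by at least 1 point (0.958 for SD 1.5; 1.111 for SD 2.0). Each scenario has 400,000 simulated participants.

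Six of the 12 scenarios, including the extremes of the Week 52 gap:

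| SD | Corr. | Switched | q4w share | Week 52 improvement, q4w / q2w | Gap | Week 52 responders, q4w / q2w | Improvement at Week 52 minus Week 24, q4w / q2w |
|---|---|---|---|---|---|---|---|
| 1.5 | 0.5 | half | 10% | 2.10 / 0.83 | 1.27 | 89% / 59% | −0.62 / +0.07 |
| 1.5 | 0.5 | all | 20% | 2.10 / 0.66 | 1.44 | 89% / 55% | −0.62 / +0.16 |
| 1.5 | 0.9 | all | 29% | 2.57 / 0.30 | 2.28 | over 99% / 47% | −0.12 / +0.05 |
| 2.0 | 0.5 | all | 26% | 2.49 / 0.62 | 1.86 | 87% / 53% | −0.72 / +0.24 |
| 2.0 | 0.9 | half | 18% | 3.04 / 0.70 | 2.33 | 99% / 54% | −0.13 / +0.03 |
| 2.0 | 0.9 | all | 35% | 3.04 / 0.06 | 2.97 | 99% / 42% | −0.13 / +0.07 |

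(Gaps were computed before rounding.) Over all 12 scenarios the gap is 1.3 to 3.0 points. The q4w group is 10% to 35% of participants: 0.10 × 25 = 2.5 to 0.35 × 25 = 8.75, so about 3 to 9 people.

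**4. What the 1-point threshold misses.** The share of q4w participants below 2 points at Week 52, minus the share below 1 point, is the share that has dropped under the entry rule but still counts as a responder. It runs from 0.096 − 0.009 = 0.087 to 0.325 − 0.111 = 0.214, so about 9% to 21%, with no true loss of response in the model.

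**The case against.** Much of the other side's case stands, and it limits how far the point can go.

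- *A reader might infer that Week 52 results are shown only as change from baseline.* They are not. SAP 4.5.2.3 also gives the responder endpoint by visit and regimen. That endpoint is still relative to baseline, with the lower threshold, so it does not remove the problem.
- *A reader might infer that every q4w participant is a Week 24 responder by definition.* The documents do not establish this. Anyone who has received SCS counts as a nonresponder afterwards (Protocol 9.3.2, SAP 4.3.2), while the stable-disease rule has no rescue condition. The endpoint uses central reading, and the documents do not say which reading decides stable disease.
- *A reader might infer that q2w holds only non-stable participants.* Switching is discretionary, so stable participants may stay on q2w. This dilutes the selection but does not remove it; the half-switched rows still show gaps of 1.3 to 2.3 points.
- *A reader might infer that the tables reveal nothing about loss of response.* A loss after Week 24 does lower the q4w mean at Weeks 40 and 52, and SAP 4.1 includes data through Week 24 in the PPE analyses. The gap is narrower: no regimen split is stated for visits up to Week 24, and no within-person change from Week 24 is defined.
- *The plan's aim is a response-guided 52-week schedule.* Change from baseline answers that, overall results are given alongside, the q4w group is openly labelled as having stable disease, and no regimen comparison or test is planned. All true. It makes this a matter of presentation, not of a wrong analysis.
- *The remedy has its own bias.* Also true: change from Week 24 shows an apparent loss in the selected group from regression to the mean alone.

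**Conclusion.** The point holds as a limit on interpretation. By-regimen NPS results at Week 52 favour q4w through selection even if the regimens do not differ, and the planned summaries do not describe directly whether response is kept after the switch.

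The direction follows from the group definitions. The size does not: 1.3 to 3.0 NPS points rests on assumed SDs and correlations, on an unbounded normal model for a 0 to 8 score, on using one measurement for both gate and outcome, and on leaving out rescue and missing data.

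For NC, LMK and TSS the advantage arises only as far as they correlate with NPS. The documents give no such correlation and it was not modelled, so a similar gap on those endpoints should not be inferred.

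The primary and key secondary Week 24 analyses are unaffected. Because the extension analysis is exploratory, descriptive and untested, this is a worthwhile improvement and not a defect that undermines the trial.

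**What to change.** In SAP 4.5.2.2 and 4.5.2.3, add within each regimen group:

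1. the Week 24 value, and the change from Week 24 to Week 52, for NPS, NC, LMK and TSS;
2. the share of Week 24 responders still improved by at least 1 point at Week 52, and the share of stable participants still improved by at least 2 points;
3. q2w participants who met stable disease, shown separately, as a listing if they are few;
4. a statement that the regimen groups are selected on response and are not to be compared.

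Two cautions belong with the table. Regression to the mean alone would produce an apparent NPS loss of about 0.1 to 0.7 points in q4w under the assumed inputs. It would also leave only about 68% to 90% of that group still at 2 points or more (1 − 0.325 to 1 − 0.096) with no true loss. And the cells will be small, perhaps 3 to 9 people on q4w.

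The cost is some extra descriptive rows and a short SAP edit. The data are already scheduled: endoscopy at Visits 4 to 9, CT at Weeks 24 and 52, and a daily diary. SAP 4.2 already counts participants who meet the 2-point criterion at both visits. No visit, procedure or dosing rule changes.
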